### Table 3 Study objectives, endpoints and estimands

Objective(s)		Endpoints/Estimands
•	To describe cell-mediated immune responses induced by the mRNA-CR-04 vaccine up to study conclusion.	
 
Frequency of CD4+/CD8+ T-cells specific for S protein encoded by the vaccine SARS-CoV-2 and WT strains measured by intracellular cytokine staining assay at each time point (D1, D15, D31, M6).
 
Cellular immune responses including, but not limited to Th1 and Th2 profiles as determined by flow cytometry using ICS at each time point (D1, D15, D31, M6).
 

•	To describe the incidence of confirmed symptomatic and asymptomatic SARS-CoV-2 infection.	
 
Percentage of laboratory-confirmed (N protein seroconversion) asymptomatic SARS-CoV-2 infection at each time point (D1, D15, D31, M6).
 
Percentage of laboratory-confirmed (RT-PCR) symptomatic SARS-CoV-2 infection at screening, D1, D8, D15, as well as at unscheduled visits.
 

•	To evaluate the genetic sequence of SARS-CoV-2 variant S protein in confirmed (RT-PCR) SARS-CoV-2 positive participants.	
 
Comparison of SARS-CoV-2 S protein genetic sequence of viral isolates (when available) to the vaccine mRNA sequence
 
Identification of SARS-CoV-2 variants.
 

•	To further characterize the humoral response (including, but not limited to functionality of antibodies) and cellular response, specific for the vaccine encoded SARS-CoV-2, WT and other relevant strains.	
 
S-specific responses at D1, D15, D31, M6
 
Other read-outs may be performed if deemed necessary.
 

Ab: Antibody; AE: Adverse event; AESI: Adverse events of special interest; D: Day; GMR: Geometric mean ratio; GMT: Geometric mean titer; ICS: intracellular cytokine staining; IgG: Immunoglobulin G; M: Month; MAAE: Medically attended adverse events; N: Nucleocapsid; pIMD: potential Immune-mediated disease; RT-PCR: Real-time polymerase chain reaction; S: Spike; SAE: Serious adverse event; VAED: Vaccine associated enhanced disease; WT: Wild type.

\*AESI include pIMDs, myocarditis/pericarditis, virologically confirmed COVID-19 cases and anaphylaxis or severe hypersensitivity within 24 hours after study vaccination (Section 8.4.4).

Details related to attributes of estimands covering intercurrent events and strategies, population, treatment condition, and population level summary will be provided in SAP.

# 4. STUDY DESIGN

# 4.1. Overall design

**Experimental Design:** Phase 1, observer-blind, randomized, placebo-controlled, multicenter, dose-escalation study to evaluate in Part A of the study, 3 doses (10  $\mu$ g, 30  $\mu$ g, and 100  $\mu$ g) of the mRNA-CR-04 (Omicron BA.5 strain) vaccine (Figure 1) in 3 groups (Group 1, Group 2 and Group 3) (Table 4). Part B of the study will commence only after all Part A participants have completed their Day 15 study visits and the Day 15 interim analysis is completed. In Part B (Table 5), 2 doses (3  $\mu$ g and 10  $\mu$ g) of the mRNA-CR-04 (Omicron BA.5 strain) vaccine will be evaluated (Figure 1). The study will be conducted in the United States (US).

Duration of the study: Approximately 6 months after dosing.

**Sentinel dosing**: In Part A of the study, each group will have 8 sentinel participants (6 receiving the mRNA-CR-04 vaccine and 2 receiving a placebo) who will be enrolled and

vaccinated in each group. The first and second sentinel participant in each group will be vaccinated and followed-up for 24 hours before the next sentinel participant can be vaccinated. Vaccination of the remaining sentinel participants in the same group will then continue with an interval of at least 60 minutes between participants. Additionally, an interval of at least 60 minutes will be maintained between the vaccination of sentinel participants across groups.

**Dose-escalation:** In Part A of the study, enrollment of participants in Group 1 and Group 2 will be done in parallel with the first participant to be enrolled in Group 1. All safety data up to Day 8 post-vaccination from sentinel participants in both groups will be reviewed by the iSRC (unblinded review). The iSRC members will determine whether any of the pre-defined holding rules are met or if there is any other safety signal. If no safety signal is observed, vaccination of the non-sentinel participants in that group will continue. If no safety signal observed from sentinel participants in Group 1 and Group 2, enrollment and vaccination of the sentinel participants in Group 3 will be initiated. In Part B, irrespective of dose, all participants in the three study groups will be enrolled in parallel.

**Safety Data:** Safety data will be collected for 6 months post-vaccination. Solicited AEs will be collected for 7 days (day of vaccination and 6 subsequent days) and unsolicited AEs will be collected up to Day 31. MAAEs, SAEs, pIMDs, and AESIs will be collected for the duration of the study. In addition to the review of unblinded data by iSRC, blinded data until Part A Day 15 interim analysis, and unblinded data subsequently, will be regularly reviewed by the SRT. For more detailed information, refer to Section 8.3 and Section 8.4.

For the vendors that will perform key study-related duties or activities, please refer to the separate list of vendors.
Table 4 and Table 5 describe the Part A and Part B study groups, interventions, and blinding, respectively.

Study	Number of	Age (Min-	Study intervention(s)	/vaccine(s) mode of	Blinding
groups	participants	Max years of age)	adminis	stration	Screening→Visit 5
	18	18 – 49	mRNA-CR-04 vaccine 10 µg	Intramuscular injection into the	
Group 1	6	18 – 49	Saline placebo (NaCl [0.9%])	deltoid muscle, preferably of the non- dominant arm.	Observer-blind
	18	18 – 49	mRNA-CR-04 vaccine 30 µg	Intramuscular injection into the	
Group 2	6	18 – 49	Saline placebo (NaCl [0.9%])	deltoid muscle, preferably of the non- dominant arm.	Observer-blind
	18	18 – 49	mRNA-CR-04 vaccine 100 µg	Intramuscular injection into the	
Group 3	6	18 – 49	Saline placebo (NaCl [0.9%])	deltoid muscle, preferably of the non- dominant arm.	Observer-blind

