# 1. PROTOCOL SUMMARY

# 1.1. Synopsis

**Rationale:** GSK is developing a novel mRNA vaccine platform where the SARS-CoV-2 Omicron variant S glycoprotein will be used as an antigen model (hereafter referred to as mRNA-CR vaccines). This mRNA vaccine platform development includes several mRNA constructs (mRNA-CR-XX) currently under development that will be progressing into clinical research in humans.

**Objectives, endpoints and estimands:** This exploratory, FTIH study is to evaluate the safety, reactogenicity and immune responses of the mRNA-CR-04 vaccine construct when administered in healthy adults previously vaccinated with SARS-CoV-2 mRNA vaccines. For details on objectives, endpoints and estimands, refer to Section 3.

**Overall design:** This will be a Phase 1, observer-blind, randomized, placebo-controlled, multicenter, dose-escalation study evaluating in Part A of the study, 3 doses ( $10 \mu g$ ,  $30 \mu g$ , and  $100 \mu g$ ) of the mRNA-CR-04 (Omicron BA.5 strain) vaccine. Approximately 72 participants will be enrolled with 24 participants per group (Group 1, Group 2 and Group 3). Within each group, participants will be randomly assigned in a 3:1 ratio to receive:

- investigational mRNA-CR-04 vaccine (SPK001-AC01 mRNA-LNP) or
- saline placebo.

For each group, 8 sentinel participants will first be enrolled and vaccinated. Enrollment of participants in Group 1 and Group 2 will be done in parallel with the first participant to be enrolled in Group 1. Only if no safety signal is observed, vaccination of the non-sentinel participants in that group will continue. If no safety signals observed in sentinel participant in Group 1 and Group 2, enrollment, and vaccination of the sentinel participants in Group 3 will be initiated. Refer to Section 4.1 and Figure 1 for more details on the study design.

Part B of the study will commence only after all Part A participants have completed their Day 15 study visits and the Day 15 interim analysis is completed. In Part B, 2 doses (3  $\mu$ g and 10  $\mu$ g) of the mRNA-CR-04 (Omicron BA.5 strain) vaccine will be evaluated. Approximately 42 participants will be enrolled in parallel in Part B and there will be no sentinel participants. Part B participants will be randomly assigned in a 3:3:1 ratio to receive:

- 3 µg investigational mRNA-CR-04 vaccine (SPK001-AC01 mRNA-LNP) or
- 10 µg investigational mRNA-CR-04 vaccine (SPK001-AC01 mRNA-LNP) or
- saline placebo.

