## 8.3.7.1. Staggered administration of study intervention

Part A of the study will be conducted in a staggered manner to ensure maximum safety of the participating participants.

- Within each group, 8 sentinel participants (6 receiving the mRNA-CR-04 vaccine and 2 receiving the placebo) will first be enrolled and vaccinated.
- Enrollment of participants in Group 1 and Group 2 will be done in parallel with the first participant to be enrolled in Group 1. The first and second sentinel participant in each group will be vaccinated and followed-up for 24 hours before the next sentinel participant can be vaccinated. If no safety concerns are identified (as confirmed through individual phone call TC1, see Table 1), vaccination of the remaining sentinel participants in the same group will then continue with an interval of at least 60 minutes between participants. Additionally, an interval of at least 60 minutes will be maintained between the vaccination of sentinel participants across groups.
- If no safety concerns are identified by the iSRC during the review of unblinded Day 8 safety data of sentinel participants from Group 1 and Group 2, the remaining participants in these groups may receive the study intervention without limitation of the number of participants per day or the time between consecutive participants. Additionally, vaccination of sentinel participants in Group 3 may be initiated.
- If no safety concerns are identified by the iSRC review of unblinded Day 8 safety data of sentinel participants from Group 3, the remaining participants in Group 3 may receive the study intervention without limitation of the number of participants per day or the time between consecutive participants.

All participants will be closely observed (visibly followed, no specific procedure) during the 60 minutes after dose administration.

In addition to iSRC, blinded data will be reviewed by the SRT. The SRT and iSRC will meet regularly to review safety data throughout the study and may request escalation to the GSB to address any potential safety concerns or study holds at any point during the study. See Section 8.3.7.3.

In Part B of the study, irrespective of dose, all participants will be enrolled in parallel, and the SRT will also be able to review unblinded data.

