#### 8.3.7.2. Outcome of safety evaluation

Outcome of safety evaluations will be documented and provided in a written way to the investigator. Refer to iSRC charter for more details.

- If **no safety** signal is observed, the favorable outcome of the safety evaluations by the iSRC will be documented and provided, authorizing the investigator to start the enrollment and study intervention administration to the remaining participants in the group and the sentinel participants in the next group.
- If a safety signal is observed during the safety evaluations or if any of the holding rules is met, the iSRC Chair is responsible for the urgent communication and escalation of the concern to the GSB. The GSB will decide and communicate whether to suspend, modify or continue the conduct of the study on all groups or on selected groups, including the rationale for the decision to put the study intervention administration on hold or not.
- The study sponsor will be accountable for notifying the decision whether to suspend, modify or continue the conduct of the study on all groups or on selected groups to the CRO. The CRO will be responsible to inform all investigators of this decision.

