### 8.3.7.3. Study holding rules

The safety holding rules are defined in the Table 12. Holding rules 1a-d will be assessed by the investigator on a continuous basis. Meeting any of these holding rules will trigger a hold of study intervention administration irrespective of number of participants enrolled and/or timing of the event. Holding rules 2a-c will be assessed by the iSRC during the safety evaluations on unblinded data.

These holding rules have been written under the assumption that the safety data from all participants will be available. If the data from all participants are not available (i.e., in case a participant is lost to follow-up), then the holding rules will be assessed on a prorata basis (expressed as percentage of participants to be evaluated) i.e., 3 out of 6 sentinel participants or 30% of all participants, whichever is met earlier.

Of note, no formal holding rules will be applied for other safety data such as non-lifethreatening SAEs, missed visits due to study intervention related AEs, Grade 1 and Grade 2 solicited and unsolicited AEs in the 7-day follow-up period (Day 1 to Day 7) and unsolicited AEs collected from Day 8 to Day 31 after study intervention administration. However, if available, these data will also be reviewed by the iSRC to allow an overall assessment of the benefit/risk ratio of study intervention administration.

Holding rule	Event (per dose and per individual study group)	Number of participants to pause vaccination in all groups, pending further evaluation by iSRC
1a	Death or any life-threatening SAE regardless of causality	≥1
1b	Any non-life-threatening SAE that cannot be reasonably attributed to a cause other than vaccination as per investigator or sponsor assessment	≥1
1c	Any withdrawal from the study (by investigator or participant request) following a Grade 3 AE	≥1
1d	Any administration site or systemic solicited AE leading to hospitalization, OR Necrosis at the injection site, Each with an event onset within the 7-day (Day 1-7) post- vaccination period	≥1
2a*	Any Grade 3 solicited administration site events, with an event onset within the 7-day (Day 1-7) post-vaccination period	≥3/6 or 30%**
2b*	Any Grade 3 solicited systemic events, with an event onset within the 7-day (Day 1-7) post-vaccination period	≥3/6 or 30%**

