#### Table 12Study holding rules

AE: Adverse event; iSRC: Internal safety review committee; SAE: Serious adverse event.

\*Refer to the FDA guidance for industry "Toxicity grading scale for healthy adults and adolescent volunteers enrolled in preventive vaccine clinical trials" [FDA, 2007]. Any laboratory parameters not listed in Section 10.2.2 will not be graded and will be assessed on case-by-case basis.

\*\*3/6 sentinel participants or 30% of all participants, whichever is met earlier.

\*\*\*2/6 sentinel participants or 10% of all participants, whichever is met earlier.

Rule 2a-2c will be analyzed and reviewed during the scheduled iSRC meetings. During these scheduled iSRC meetings, iSRC will decide to:

- allow for dosing of the remaining non-sentinel participants (12 receiving mRNA-CR-04 and 4 receiving placebo) within the same group
- allow for randomization of the sentinel participants in the next group.

More details on the composition, objectives, and responsibilities of the iSRC, and the schedule and conduct of the iSRC meetings will be described in the iSRC charter.

If a holding rule is met, the investigator must suspend enrollment and administration of the study intervention and inform the CRO team immediately (holding rules 1a-d). Refer to Table 16 for contact information.

The CRO team will inform the investigator if holding rules 2a-c are met. Investigators will be responsible to inform the IRB/IEC if a holding rule has been met.

The following communication sequence must be followed when a holding rule 1a-1d is met:

- The concerned site staff must put study intervention randomization and administration on hold.
- The concerned site staff must immediately inform the CRO team contact defined in the Section 8.4.6.
- Enrollment and intervention allocation through IRT will be stopped on a study level.
- The CRO team will inform all investigators about the stopping of enrollment and intervention.
- All informed site staff will confirm to the CRO team that action has been taken providing appropriate documentation to the CRO team.
- The CRO team will inform GSK and provide the blinded data to GSK's CSL for further SRT and GSK GSB review.
- The CRO team will forward the relevant unblinded safety information to iSRC for evaluation.

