#### **Risk assessment:**

- Figure 2 illustrates that with 6 participants receiving the mRNA-CR-04 vaccine per group:
  - Rule 1: when at least 1 SAE is observed within 6 participants receiving the mRNA-CR-04 vaccine, there is 90% probability of not holding for a 1.7% SAE true incidence and 80% (=1-20%) probability of holding it for an SAE true incidence >23%.
  - Rule 2a-2b: when at least 3 participants with an AE are observed within 6 participants receiving the mRNA-CR-04 vaccine, there is 90% probability of not holding for a 20% AE true incidence and 80% (=1-20%) probability of holding it with a true AE incidence >58%.
  - Rule 2c: when at least 2 participants with an AE are observed within 6 participants receiving the mRNA-CR-04 vaccine, there is 90% probability of not holding for a 9% AE true incidence and 80% (=1-20%) probability of holding it with a true AE incidence >42%.
  - With 18 participants receiving the mRNA-CR-04 vaccine, and rule 1 (1/18), there is 90% probability of not holding for a 0.59% AE true incidence and 80% (=1-20%) probability of holding it with a true incidence >8.5%.

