# Figure 2 Probability of not meeting holding rules 1 and 2 for 8 participants per study group

## 8.3.7.4. SRT and iSRC evaluation

The study will be overseen by an iSRC operating under a charter. Core members of the iSRC will include a GSK safety physician, a CSL and a biostatistician who are not otherwise involved in the conduct of the project. The iSRC safety reviews will be conducted using unblinded data. The iSRC will have access to the participant randomization and will review unblinded data.

In addition to the iSRC, the project SRT will review blinded data until the Part A Day 15 interim analysis, and unblinded data subsequently, on a regular basis throughout the study.

The iSRC will review accumulated unblinded safety data of the sentinel participants of each group up to 7 days post-vaccination. The iSRC will include all safety data sources in their Day 8 safety review (i.e., solicited safety data, unsolicited safety data, SAEs and AESIs, as well as laboratory safety data). If no pre-defined holding rule is met (refer to Section 8.3.7.3) or if no safety signal is observed the remaining participants in the group can be vaccinated and vaccination in the next group can be initiated.

In case the iSRC, through the in-stream data monitoring of all the accumulated safety data available detects that a holding rule is met, the study vaccination will be temporarily paused in all study groups and sites pending review of safety data by the iSRC. The iSRC will make relevant recommendations to the GSB chair(s), who will make the final decision whether vaccination can be safely resumed or not.

In addition, at any time during the study, if one of the holding rules 1a through 1d (refer to Table 12 for details) is met, the investigator will immediately inform the CRO team. Vaccination will be paused and an urgent ad-hoc meeting of the iSRC will be called to thoroughly review the event(s) and recommend to the GSB whether vaccination can be safely resumed or not. The GSB chair(s) will make the final decision whether vaccination can be safely resumed or not.

In Part B of the study, the iSRC will only be requested to review unblinded data if a study holding rule is met or if the SRT identifies a safety concern through in-stream data monitoring of unblinded data.

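### Protocol 8.3.7.4 joins the two Part A dose-release conditions with *or*, where the rest of the protocol needs both; the release wording for Groups 1 and 2 also differs between sections

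*Protocol*

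**What the plan says.** In Part A each group starts with 8 sentinels (6 vaccine, 2 placebo). Groups 1 (10 µg) and 2 (30 µg) run in parallel. Under Protocol 4.1 the iSRC reviews unblinded Day 8 sentinel data from both groups and looks for met holding rules and for any other safety signal. The conditions for continuing appear in several places:

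- **8.3.7.4:** "If no pre-defined holding rule is met (refer to Section 8.3.7.3) or if no safety signal is observed the remaining participants in the group" may go on to dosing, and the next group may start.
- **8.3.7.2, first bullet:** when there is no signal, the iSRC's favourable outcome is documented in writing, "authorizing the investigator to start the enrollment and study intervention administration to the remaining participants in the group" and to the next group's sentinels.
- **8.3.7.2, second bullet:** a signal or a met holding rule is escalated urgently to the GSB, which decides whether to suspend, modify or continue, for all groups or for selected ones.
- **1.1:** "Only if no safety signal is observed, vaccination of the non-sentinel participants in that group will continue".
- **4.1:** the same sentence as in 1.1, without its opening word: "If no safety signal is observed, vaccination of the non-sentinel participants in that group will continue".
- **8.3.7.1:** if the iSRC finds no concern in the Day 8 data of sentinels "from Group 1 and Group 2, the remaining participants in these groups may receive the study intervention without limitation" on daily numbers or spacing. The same condition opens Group 3 (100 µg).
- **Text under Table 12:** the iSRC may "allow for dosing of the remaining non-sentinel participants (12 receiving mRNA-CR-04 and 4 receiving placebo) within the same group".

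Table 12 and 8.3.7.4 pause vaccination in all groups once a holding rule is met. For events outside the rules, 8.3.7.3 says that "no formal holding rules will be applied for other safety data", such as Grade 1 and 2 events, although the iSRC reviews those data where available.

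**The concern.** The holding rules and the iSRC's judgement of a signal are two separate safeguards. The rules are counts fixed in advance; the signal judgement covers whatever the counts miss. Joining the two conditions with *or* means that satisfying one is enough, so the second safeguard no longer blocks anything. The sentence governs both the rest of the current group and the start of the next, so it reaches the escalation to 100 µg in a first-in-human study.

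The second issue is narrower. With two groups dosed in parallel, the protocol should say whether a signal in one group's sentinels holds the other group while the GSB considers it. One section sets a joint condition, three places use single-group wording, and none states an interim hold for a signal that meets no rule.

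**Working it through.** **1. The *or* in 8.3.7.4.** There are two findings, holding rule met (yes/no) and signal observed (yes/no), and so four outcomes.

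| Rule met | Signal | 8.3.7.4 release sentence, literal | 8.3.7.2 |
|---|---|---|---|
| no | no | release | release |
| no | yes | **release** | escalate to GSB |
| yes | no | **release** | escalate to GSB |
| yes | yes | no release | escalate to GSB |

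The two sections disagree in the middle rows. The third row is closed elsewhere: Table 12 and the next paragraph of 8.3.7.4 pause all groups when a rule is met. The second row has no automatic pause. There, 8.3.7.4 stands against 8.3.7.2, 4.1 and the *only if* in 1.1.

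**2. Do the holding rules alone make the second row unimportant?** The risk assessment in 8.3.7.3 gives the operating characteristics for 6 vaccinated sentinels. For rule 2c (at least 2 of 6) it says "there is 90% probability of not holding for a 9% AE true incidence". Exact binomial calculation reproduces its figures:

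- Rule 2c, no hold at 9%: 0.91^6 + 6 × 0.09 × 0.91^5 = 0.568 + 0.337 = 0.905. Hold at 42%: 0.797.
- Rules 2a-2b (at least 3 of 6), no hold at 20%: 0.8^6 + 6 × 0.2 × 0.8^5 + 15 × 0.2^2 × 0.8^4 = 0.262 + 0.393 + 0.246 = 0.901. Hold at 58%: 0.792.
- Rule 1 (at least 1 of 6), no hold at 1.7%: 0.983^6 = 0.902. Hold at 23%: 1 − 0.77^6 = 0.792.

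These agree with the stated 90% and 80%. With six vaccinees the count-based rules 2a-2c reach about 80% probability of holding only at a true incidence of 42% or 58%. The signal judgement therefore has a real job, and the release sentence should not bypass it. The figures do not say how often a signal would arise; the documents give no definition or rate from which to calculate that.

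**3. Groups 1 and 2: joint or separate?**

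| Sentinel result, no holding rule met | 8.3.7.1 | 1.1, 4.1, text under Table 12 | 8.3.7.2 |
|---|---|---|---|
| Both clean | both groups released | both released | favourable outcome |
| Signal at 10 µg, 30 µg clean | condition not satisfied; consequence not stated | 30 µg can be read as released | GSB decides, all or selected groups |
| 10 µg clean, signal at 30 µg | condition not satisfied; consequence not stated | 10 µg can be read as released | GSB decides, all or selected groups |

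In 1.1 and 4.1 the sentence after the single-group wording states the joint Group 1 and Group 2 condition, but only for opening Group 3. That contrast makes the group-by-group reading natural. The second row matters more, because the clean group would receive three times the dose at which the signal was seen.

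**The case against.** The strongest reply is that no one working from the whole protocol would act on the literal *or*. Section 8.3.7.2 ties the written authorisation to the absence of a signal and sends any signal to the GSB; 4.1 has the iSRC assess both conditions. On this view the *or* is a slip with little practical force. Most of that stands, and it limits the weight of the point. It does not make the sentence correct: the repeated *if* makes the two conditions alternatives, and 8.3.7.4 is the section that describes the iSRC's own evaluation.

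Three stronger readings are tempting, and the documents do not support them.

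- *Sites would have to choose between release rules.* They would not. One unblinded iSRC reviews both groups, and the investigator acts on its written outcome (8.3.7.2).
- *Section 8.3.7.1 forbids releasing one group alone.* It gives a sufficient condition for releasing both and is silent on a split result, so it differs from the other wording without strictly excluding it.
- *Twelve more people would receive 30 µg after a signal at 10 µg, with a calculable probability.* Such a signal already goes to the GSB, which may act on all groups or selected ones. Falling one event short of a rule is not a signal, and any probability would rest on assumed rates.

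What remains of the second issue is the absence of a stated interim hold on the other group.

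**Conclusion.** The point holds as a wording error in a dose-release rule, with a smaller inconsistency beside it. Section 8.3.7.4 contradicts 8.3.7.2, 4.1 and 1.1 for a signal that meets no holding rule, and it should require both conditions. The unit affected by each release is 16 non-sentinels (12 vaccine, 4 placebo) or, for escalation, the 8 Group 3 sentinels (6 vaccine, 2 placebo). No sample-size figure, holding-rule probability or planned analysis changes, and the gravest events are unaffected because rules 1a-1d pause all groups at one case.

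Limits: the iSRC charter is a separate document and Figure 1 is not shown in the available text; either may already settle the matter. The point concerns Part A, since Part B has no sentinels and enrols all groups in parallel. Part B starts only after all Part A Day 15 visits, and the documents give no dosing dates. If Part A dosing is complete, what remains is to confirm which condition was applied and not to carry the sentence into later protocols.

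**What to change.** 1. In Protocol 8.3.7.4, replace *or if no* with *and no*, so that release and the start of the next group require both no met holding rule and no safety signal.
2. Use one release wording for Groups 1 and 2 in 1.1, 4.1, 8.3.7.1 and the text under Table 12.
3. Add to 8.3.7.1 that a signal in Group 1 (10 µg) sentinels, even short of a holding rule, holds Group 2 (30 µg) non-sentinel dosing until the GSB decides under 8.3.7.2. A signal seen only at 30 µg can stay with the existing GSB decision.
4. Check that the iSRC charter says the same.

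Item 1 corrects an error and costs nothing. Items 2 and 3 settle a choice that the protocol leaves open; their price is a possible short delay to a clean 30 µg group. No participants, visits or data are added.
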